### **8.2.1.1 Proportion of patients with mean UFC $\leq$ ULN**

Analysis of all patients

In general, UFC is determined by collecting two or three 24-hour urine samples and calculating the mean of the 24-hour UFC values. However, routinely some sites may also use only one single 24-hour urine sample to assess UFC. Therefore in this study, mean UFC (mUFC) refers to the mean if more than one 24-hour UFC value was reported within 2 weeks and to the single value if only one value was reported.

If a 24-hour urine collection was performed but 24-hour UFC was not documented, 24-hour UFC will be calculated as product of 'urinary cortisol, random' (concentration of cortisol in 24-hour urine) and the total volume of 24-hour urine, if available.

For each time window (Month 1, 3, 6, 9, 12, 18, 24, 30 and 36), the number and proportion of patients with mean UFC (mUFC)  $\leq$  ULN will be presented together with corresponding exact (Clopper-Pearson) 95% confidence intervals (CI) for the proportions. The proportion will be calculated relative to the number of patients with a value for the respective time point (mUFC and ULN).

In addition, the number of patients without mUFC value and the number of patients with missing ULN (but mUFC value available) will be displayed by time window. In each time window, only those patients will be included who were treated during that window and followed up until the end of the respective time window.

Analysis of patients who discontinued pasireotide s.c.

A similar analysis will be performed for the subgroup of patients who discontinued pasireotide s.c. prematurely and had an assessment on-treatment and 90 days after last dose. The statistics described above will be displayed for the patient's last value on treatment and for the last value assessed during the 90 days after last dose. Furthermore, the status of the last mUFC value on treatment ( $\leq$  ULN,  $>$  ULN) will be cross-tabulated against the status 90 days after last dose.

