3.1.2 Efficacy assessments

All efficacy assessments will be collected from patient's enrollment into this study until the last follow-up visit for patients who complete the 3-year observation period or until 3 months after the last dose for patients who permanently discontinue pasireotide s.c. prior to completing the 3-year observation period.

- Urinary Free Cortisol (UFC). In general UFC is determined by collecting two or three 24-hour urine samples and calculating the mean. However routine site procedures may also only foresee one single urine sample to assess UFC. The frequency of UFC determination will probably vary from the initiation of treatment (when UFC values will be performed more frequently than at monthly interval) as compared to the time after obtaining control.
- Biochemical measures of disease activity: serum cortisol, serum cortisol after dexamethasone testing, salivary cortisol, plasma ACTH and fasting serum lipid profile.
- Measures of clinical signs and symptoms: Blood pressure, body weight, body mass index, waist circumference, clinical symptoms of Cushing's disease.
- Changes in tumor size as measured by MRI or other imaging techniques
- Changes in the quality of life score determined from a patient reported quality of life questionnaire (Cushing QoL and EURO QoL).

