The data will be summarized with respect to demographic and baseline characteristics, safety observations and measurements as well as efficacy assessments. Data will be summarized and displayed by time intervals based visit windows rather than by a strict visit schedule, in order to reflect the nature of this study. Details on definition of time windows will be provided in the Report and Analysis Plan (RAP). Furthermore, for patients who discontinue treatment prior to the 3-year observation period, their safety and efficacy parameters will be reported according to the time window that corresponds to 90 days from the Day of last dose of pasireotide s.c. Continuous variables will be summarized by number of patients, mean, standard deviation, minimum, median and maximum. Categorical variables will be summarized by absolute and relative frequencies. Counts of missing values for both continuous and categorical variables will be reported. Results with and without imputation will be reported.

Baseline assessment refers to the last assessment prior to the patient's first pasireotide s.c. dose recorded after the signing of the informed consent or acknowledging an equivalent document (e.g., written information) as per country regulation. For some assessment this definition maybe expanded to include the first assessment post the first pasireotide s.c. dose recorded after informed consent or an equivalent document (e.g., written information) as per country regulation.

In this study, the first analysis will occur at about 12 months after the first patient enters the study. After this first analysis there will be one analysis on a yearly basis. The final analysis will occur when all patients complete the study. The same analysis will be performed for all analyses time points.

Assessment time points are considered relative to first pasireotide s.c. dose recorded on or after the singing of the informed consent or acknowledging of an equivalent document (e.g., written information) as per country regulation, unless noted otherwise.

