6.5.1.1 Proportion of patients with mUFC \leq ULN

In general UFC is determined by collecting two or three 24-hour urine samples and calculating the mean. However, routinely some sites may also use only one single urine sample to assess UFC. In this study, if there are two or three assessments of UFC within 24-hours, then mean UFC refers to mean of these UFC assessments. In contrast, if what is available is just one assessment, then mean UFC refers to this single assessment. At each specified visit window (month 1, 3, 6, 12, 24 and 36) the number and percentage of patients with mean UFC \leq ULN will be presented together with corresponding exact 95% confidence interval (CI).

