### 6.1.6 Baseline definition

The last non-missing assessment before or on the day of the patient's first dose during the study is considered the baseline assessment.

If no assessment is available before or on the day of first dose, the missing assessment may be imputed by the earliest post-dose assessment, provided it was performed within a pre-defined time window after first dose and before end of treatment.

Time windows depend on the type of assessment; they are displayed in Table 6-1. Baseline values assessed after first dose will not be used as post-baseline assessments.

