**Table 6-1 Time window for baseline assessments (only for cohort 2)**

Type of assessment	Time window after first dose (1)
Vital signs	0 day
ECG	1 week
Pituitary imaging	6 months
Gallbladder imaging	6 months
Quality of Life questionnaires	6 months
Assessment of clinical symptoms of Cushing's disease	1 week
Salivary cortisol	1 week
Blood sample for efficacy parameters (serum cortisol, ACTH, lipids)	1 week
Blood sample for safety tests (hematology, blood chemistry, hormones)	0 days
24-hour urine collection for UFC determination	1 week

(1) Assessments performed during this time window after first dose are accepted as baseline assessment if no assessment was performed before or on the day of the first dose.

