### 6.1.7 Time windows

There is no visit schedule and no planned assessment in this non-interventional study. Assessment related data are collected as they become available during the study period. Therefore assessments are assigned to time windows based on the study day on which the assessment is performed. For mean UFC, the sample day of the first urine sample included in the calculation of mean UFC will be used for assignment to time windows.

If there are multiple values within a time window, the assessment closest to the target day of the time window will be used, if not indicated otherwise. If two assessments are equally close (e.g. 7 days before and 7 days after target day), the later will be used.

Time windows will be assigned according to the window schema in Table 6-2 if assessments are expected more frequently than every 6 months. Otherwise the time windows in Table 6-3 will be applied (e.g., for tumor volume, variables related to patient reported outcome questionnaires, findings of gallbladder ultrasound).

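### The 2-week averaging rule for mean UFC does not stop at the first in-study dose, so an on-drug sample can enter a new user's baseline mean

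*SAP*

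**What the plan says.** Three SAP rules act together:

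- **Averaging (SAP 8.2.1.1):** "mean UFC (mUFC) refers to the mean if more than one 24-hour UFC value was reported within 2 weeks"; a lone value stands for itself. The text does not say where the 2 weeks start.
- **Dating (SAP 6.1.7):** "the sample day of the first urine sample included in the calculation of mean UFC will be used for assignment to time windows".
- **Baseline (SAP 6.1.6):** "The last non-missing assessment before or on the day of the patient's first dose during the study is considered the baseline assessment". A post-dose value may stand in only when there is no earlier one. Table 6-1, whose title limits it to cohort 2, allows 1 week for the row "24-hour urine collection for UFC determination".

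The protocol differs on averaging. Its Section 6.5.1.1 says "if there are two or three assessments of UFC within 24-hours, then mean UFC refers to mean of these UFC assessments", and otherwise uses the single value. On baseline, the introduction to protocol Section 6 says "Baseline assessment refers to the last assessment prior to the patient's first pasireotide s.c. dose recorded after the signing of the informed consent", and allows this to be widened for some assessments.

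SAP 4.1 says the analysis follows protocol Section 6. SAP Section 3 declares no change to the planned analysis.

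**The concern.** A baseline should describe the patient before the drug acts. In new users (cohort 1), a mean that begins before the first dose and takes in urine collected on drug is pulled toward the treated level if UFC has begun to fall. It still carries a pre-dose date and so passes as baseline. Change from baseline in mean UFC (SAP 8.2.1.2) is then understated for that patient, and the baseline covariate in the mixed model (SAP 6.2.3) carries the same error.

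There is a second effect. An on-drug sample used in a baseline-dated mean may no longer be available to the Month 1 window (Day 2 to 60), so a patient with few samples could appear there as missing.

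The result also runs against the SAP's own intent. Table 6-1 keeps post-dose UFC out of baseline except in a narrow fallback, and the averaging rule lets it in without that limit.

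Samples on both sides of the first dose are plausible: protocol 3.1.2 describes treatment initiation as the time "when UFC values will be performed more frequently than at monthly interval".

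**Working it through.** The plan gives no figure to reproduce here. The check traces the rules and then illustrates the size.

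**1. One example through the rules.** Take a new user with UFC on Day -3 and Day 8. SAP 6.1.5 has no Day 0, so these are 3 days before and 7 days after the first dose: 3 + 7 = 10 days apart, which is within 2 weeks. By 8.2.1.1 they form one mean. By 6.1.7 the mean is dated Day -3. By 6.1.6 it is the baseline, if it is the last assessment dated on or before Day 1.

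**2. How far the rule reaches.** Reading the 2 weeks as 14 days from the first sample in the set:

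| First sample | Last day that can enter the mean |
|---|---|
| Day -7 | Day 8 |
| Day -1 | Day 14 |
| Day 1 | Day 15 |

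The Table 6-1 fallback stops at 1 week (Day 8) and is for cohort 2 only. A fallback mean first sampled on Day 8 could itself run to Day 8 + 14 = Day 22.

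**3. Size for one affected patient.** Set the true pre-dose level to 1. Inputs:

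- True later change: -47%, so the later level is 0.53. This is the approximate median fall in the phase III study (protocol Section 1), used only as an illustration.
- Early on-drug sample: lower by r = 25% or 47%. Both values are assumptions; the documents give no fall for the first two weeks.

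Mixed baseline B = (pre + post × (1 - r)) / (pre + post), where pre and post are the numbers of samples. Reported change = 0.53 / B - 1.

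| Samples (pre + on-drug) | r | B | Reported change |
|---|---|---|---|
| 1 + 1 | 25% | 1.75/2 = 0.875 | -39% |
| 1 + 1 | 47% | 1.53/2 = 0.765 | -31% |
| 2 + 1 | 25% | 2.75/3 = 0.917 | -42% |
| 2 + 1 | 47% | 2.53/3 = 0.843 | -37% |

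With only pre-dose samples B = 1 and the reported change is -47%. If UFC has not yet fallen (r = 0) there is no distortion. If the early sample is higher than the pre-dose one, the error reverses.

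**4. Dilution across the cohort.** Suppose every patient's true change is -47% and a share s has the largest distortion above (-30.7% before rounding). The cohort mean change is -47 + s × 16.3 percentage points. For s = 10% (an assumption) that is -45.4%; for s = 25%, -42.9%. SAP 8.2.1.2 places its confidence intervals on the median, which a few mixed baselines would move little.

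**5. End of treatment.** SAP 8.2.1 limits efficacy values to 3 days after the end of treatment, and Table 6-2 opens the follow-up window on the next day. Applied to each sample, this separates on-drug from off-drug urine. Applied to a mean dated by its first sample, it does not: a mean first sampled at last dose + 3 days could reach last dose + 17 days (3 + 14). The SAP does not say which is meant.

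**The case against.** The best defence is that no programmer would do this. SAP 6.1.6 confines baseline to assessments on or before the first dose, so with a Day -3 sample in hand there is no reason to reach for Day 8. That is a sensible reading, but the SAP does not state it. For UFC the unit assessed is the mean, and 6.1.7 fixes the mean's date by its first sample only.

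Other parts of the defence stand, and they rule out stronger readings that a reader might infer:

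- **That mixing will occur.** The documents do not show this. Protocol 3.1.2 makes it plausible, but Table 3-1 suggests UFC at baseline and then monthly for the first 3 months, a spacing that would usually keep samples apart.
- **That the cohort result is understated by the amounts in the table.** Those are figures for one affected patient under assumed early falls.
- **That the last on-treatment value is contaminated.** The 3-day limit may well be meant per sample, so the text there is ambiguous rather than wrong.
- **That the proportion with mean UFC at or below the ULN is biased through baseline.** It uses no baseline. Its only exposure at the start of treatment is the possible loss of early samples from Month 1.
- **That the protocol's rule should be restored.** Two or three separate 24-hour collections cannot fit within 24 hours, so the SAP was right to replace it. What is missing is a record of the change.

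**Conclusion.** The gap is real, and a short change to the text closes it. Read literally, SAP 8.2.1.1, 6.1.6 and 6.1.7 let on-drug urine into a cohort 1 baseline, contrary to the limits in Table 6-1. Cohort 2 is much less exposed because those patients are already on the drug at entry. The affected results are change from baseline in mean UFC (8.2.1.2) and the mixed-model covariate, with a possible loss of Month 1 values.

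Where it happens and UFC has already fallen, the bias is toward no change. It amounts to 5 to 16 percentage points on a true -47% in the illustrated cases (-42% to -31%). This rests on the assumed early falls of 25% to 47% and on a later level that holds at -47%. The share of patients affected is unknown, so no cohort-level figure can be given. The study is exploratory, so no formal test is at stake.

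**What to change.** In SAP 8.2.1.1:

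1. Average only samples within 2 weeks of the first sample in the set that all fall in one period: on or before Day 1; after Day 1 up to last dose + 3 days; or later.
2. Apply the 3-day limit to individual samples before averaging.
3. Keep the Table 6-1 fallback for cohort 2, using only samples inside its 1-week window.

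In SAP Section 3, replace the not-applicable entry with a statement that this rule supersedes the 24-hour rule in protocol 6.5.1.1, and why.

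The cost is a few lines of SAP text and a date check in the derivation. Some means will rest on fewer samples and be somewhat noisier, but 8.2.1.1 already accepts a single value as the mean.

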2.2 Secondary objectives

- To document the short and long-term efficacy of pasireotide s.c. as measured by the proportion of patients that reach mean UFC \leq ULN at 1, 3, 6, 12, 24 and 36 months after enrolling into the study
- To document the changes of biochemical measures of disease activity (mean UFC, serum cortisol, serum cortisol after dexamethasone testing, salivary cortisol, ACTH and fasting serum lipid profile) over time
- To document normalization of biochemical measures of disease activity (serum cortisol, serum cortisol after dexamethasone testing, salivary cortisol and ACTH) over time, where normalization refers to being within the upper and lower limit of normal ranges
- To document the changes of measures of clinical signs and symptoms (blood pressure, body weight, body mass index, waist circumference) over time
- To document the changes in clinical symptoms of Cushing's disease over time
- To document the changes in safety and efficacy parameters over a period of 3 months after discontinuing pasireotide s.c. treatment for patients that permanently discontinue pasireotide s.c. prior to completing 3-year observation period
- To document the changes in tumor size over time
- To document the changes in patient-reported outcome questionnaires (Cushing QoL and EURO QoL)
- To document the overall safety and tolerability of pasireotide s.c.

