3.4.1.1 Treatment discontinuation

Patients who permanently discontinue treatment with pasireotide s.c. prior to the 3-year observation period will have to be withdrawn from this study. Patients who discontinue pasireotide s.c. treatment because of an adverse event, must be followed by the investigator until resolution of the AE or until 3 months following discontinuation of drug whichever is longer.

All available safety and efficacy parameters will be collected for a period of 3 months following the last dose of pasireotide s.c. for patients who permanently discontinue pasireotide s.c. prior to completing the 3-year observation period.

Patients may voluntarily withdraw from this study or discontinued at the discretion of the investigator at any time. If such withdrawal occurs the investigator should determine the primary reason for a patient's premature withdrawal from this study. The withdrawal reason should be categorized into one of the following:

- Adverse event(s)
- Protocol deviation
- Subject withdrew consent or equivalent document (e.g., written information) as per country regulation
- Lost to follow-up
- Administrative problems
- Death
- Unsatisfactory therapeutic effect

For patients who are lost to follow-up, the investigator should show "due diligence", for the first 3 months after the last known date the patient took pasireotide, by documenting in the source documents steps taken to contact the patient, e.g. evidence of two certified letters, dates of telephone calls, sent emails.

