6.5.1 Efficacy evaluation

The secondary efficacy analysis will be performed on the FAS.

The secondary efficacy endpoints are as follows:

- Proportion of patients with a mean UFC \leq ULN at 1, 3, 6, 12, 24 and 36 months after enrolling into the study
- The absolute and percentage change from baseline in biochemical measures of disease activity (mean UFC, serum cortisol, serum cortisol after dexamethasone testing, salivary cortisol, ACTH and fasting serum lipid profile) over time
- Proportion of patients achieving normalization of biochemical measures of disease activity (serum cortisol, serum cortisol after dexamethasone testing, salivary cortisol, and ACTH) over time, where normalization refers to being within the upper and lower limit of normal ranges
- The absolute and percentage change from baseline in clinical signs and symptoms (blood pressure, body weight, body mass index, waist circumference) over time
- The proportion of patients with favorable shift from baseline in clinical symptoms of Cushing's disease over time
- The change from the last dose of pasireotide s.c. to 3 months after permanent discontinuation of pasireotide s.c. for patients that discontinue pasireotide s.c. prior to completing the 3-year observation period. This change will be evaluated for all available continuous safety and efficacy parameters
- The absolute and percentage change from baseline in tumor size over time
- The absolute and percentage change from baseline in patient reported outcome questionnaires (Cushing QoL and EURO QoL) over time

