### 7.2 DEFINITION OF POPULATIONS FOR ANALYSIS

#### 7.2.1 Full Analysis Set

The Full Analysis Set (FAS) comprises all patients who have signed informed consent (or acknowledged an equivalent document) and have been treated with pasireotide s.c. after enrollment into the study.

The full analysis set will be used for all efficacy analyses.

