Except for the analysis of change from end of treatment to 90 days later, the efficacy analyses will only consider on-treatment values, defined as values assessed before end of treatment + 3 days.

All assessments will be assigned to time windows based on the study day on which the assessment was performed. If there are multiple values within a time window, the assessment closest to the target day of the time window will be used, if not indicated otherwise. Further details including the start and end days of the time windows are available in Appendix 16.1.9 of the CSR.

The continuous efficacy parameters will be also evaluated through a couple of sensitivity analyses: the first will be imputing the worst value at that time window in case of missing data and the second on the patients with the full set of values. The same Mixed Model will be employed for both the analyses.

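### The mUFC ≤ ULN proportion counts only patients still treated and measured, so the Month 12–36 figures can rise or fall with selective stopping, and no version of the endpoint accounts for stoppers

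*SAP*

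**What the plan says.** **Objective.** Protocol 2.2 opens its secondary objectives with "To document the short and long-term efficacy of pasireotide s.c. as measured by the proportion of patients that reach mean UFC" at or below ULN, at 1, 3, 6, 12, 24 and 36 months after enrolling.

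**Analysis set.** Protocol 6.5.1: "The secondary efficacy analysis will be performed on the FAS". SAP 7.2.1: "The full analysis set will be used for all efficacy analyses".

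**Stopping treatment.** Protocol 3.4.1.1: "Patients who permanently discontinue treatment with pasireotide s.c. prior to the 3-year observation period will have to be withdrawn from this study". Data are then collected for only 3 months after the last dose. Seven withdrawal reasons are listed, one of them "Unsatisfactory therapeutic effect".

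**Eligible values.** SAP 8.2.1, leaving aside the comparison with 90 days after the last dose: "the efficacy analyses will only consider on-treatment values, defined as values assessed before end of treatment + 3 days".

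**Denominator.** SAP 8.2.1.1: "The proportion will be calculated relative to the number of patients with a value for the respective time point (mUFC and ULN". The counts of patients with no mUFC value or no ULN are shown by window, but in each window "only those patients will be included who were treated during that window and followed up until the end of the respective time window".

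**Sensitivity analyses.** Protocol section 6 says results will be given with and without imputation. Protocol 6.5.1.5 provides for sensitivity analyses of the efficacy endpoints and leaves their detail to the analysis plan. SAP 8.2.1 defines two, worst-value imputation and complete cases, both for continuous parameters. SAP section 3 records no change to the planned analysis.

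**The concern.** The endpoint is worded as control at fixed times after enrolment and is assigned to the FAS. The calculation rules turn it into control among patients who are still on pasireotide and were measured. A reader of the Month 12, 24 and 36 rows would see a series of percentages and naturally read it as the course of efficacy in the enrolled population. In fact the population changes from row to row, and part of that change may depend on the outcome, since lack of effect is itself a recorded reason for leaving.

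At stake is the interpretation of the only efficacy endpoint for which the protocol fixes time points out to three years. A move between Month 6 and Month 36 could reflect who stayed rather than any change in disease control, and nothing planned for this endpoint would separate the two.

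**Working it through.** The documents give no expected mUFC rate or stopping rate for this study, so there is no figure of the plan's own to reproduce.

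**Step 1: follow one patient through the rules.** Suppose the last dose is at Month 5, about Day 152 (5 × 30.4375).
- On-treatment efficacy values end at about Day 155 (last dose + 3 days).
- SAP Table 6-2 runs the Month 6 window from Day 137 to Day 229. The patient may still count there if an on-treatment value exists.
- The Month 9 window starts on Day 230. From there on the patient has no eligible value and was not treated in the window. He or she is therefore out of the numerator, the denominator and the count without an mUFC value.

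This holds however the condition on follow-up to the end of the window is read.

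**Step 2: formulas.** Let *r* be the share controlled before attrition, and *d*C and *d*U the shares of controlled and uncontrolled patients who have stopped by the window. Hold each patient's control status fixed and assume everyone still treated has a value.
- SAP proportion = *r*(1 − *d*C) / [*r*(1 − *d*C) + (1 − *r*)(1 − *d*U)]
- Share of enrolled patients on drug and controlled = *r*(1 − *d*C)

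The SAP proportion exceeds *r* if and only if *d*U > *d*C, and equals it when they are equal.

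**Step 3: illustration with 100 patients, 20 controlled.** The 20% is an assumption lying between the 14.6% and 26.3% that the protocol's Introduction quotes for Month 6 of the phase III study. The stopping rates are assumptions too.

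| Stopped: controlled / uncontrolled | Remaining: controlled + uncontrolled | SAP proportion | On drug and controlled, of 100 |
|---|---|---|---|
| 30% / 70% | 14 + 24 | 14/38 = 37% | 14% |
| 40% / 60% | 12 + 32 | 12/44 = 27% | 12% |
| 50% / 50% | 10 + 40 | 10/50 = 20% | 10% |
| 60% / 20% | 8 + 64 | 8/72 = 11% | 8% |

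**Step 4: sensitivity to the starting rate and N.** Here 20% of controlled patients stop and 40%, 60% or 80% of uncontrolled patients stop.
- N = 200, 53 controlled at the start (26.5%): 42/130 = 32.3%, 42/101 = 41.6%, 42/71 = 59.2%. Over all 200 it is 42/200 = 21.0% each time. The exact 95% intervals are 24.4–41.1, 31.9–51.8 and 46.8–70.7, against 15.6–27.3.
- N = 100, 15 controlled at the start: 12/63 = 19.0%, 12/46 = 26.1%, 12/29 = 41.4%. Over all 100 it is 12.0%.

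Reversing the selection (60% of controlled and 20% of uncontrolled stopping) with N = 200 and 53 controlled gives 21/139 = 15.1%, below the 26.5% start.

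**The case against.** - **An on-treatment proportion is a legitimate descriptive quantity, and Protocol 6.5.1.1 fixes no denominator.** This stands. The fault is that the conditional figure is unlabelled and is the only version of an endpoint assigned to the FAS.
- **The SAP discloses the attrition.** Partly true. SAP 8.2.1.1 has a separate table of premature discontinuers, SAP 4.2.1 tabulates discontinuations and reasons on the FAS, and SAP 4.1.1 reports the analysis-set sizes. Because the number controlled is shown per window, a reader of the final report could divide it by the FAS count. But the discontinuer table needs both an on-treatment and a 90-day value, pools all stopping times and is not combined with the windowed rate. The disposition table is not split by window or mUFC status.
- **Continuous mUFC has a mixed model and a worst-value analysis.** True, but these yield means rather than the proportion controlled, and the SAP does not say whether windows after stopping count as missing.
- **Counting every stop as not controlled is itself a choice.** This stands. It merges administrative and consent withdrawals with treatment failure, and under equal 50% stopping it halves the figure with no change in control. It is therefore proposed only as a supplement, with stops split by reason. Nor does it undo earlier selection in Cohort 2, whose patients were already on pasireotide at entry.
- **The study is exploratory, with no primary efficacy endpoint.** This limits the weight of the point but does not remove it.

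A reader might infer that the reported rate must rise with attrition, or that the design removes failures in particular. The documents do not support this. Withdrawal follows permanent discontinuation for any reason, adverse events included. Protocol 3.5.2.3 lists hypocortisolism as an identified risk, so well-controlled patients may also stop.

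**Conclusion.** The point holds. From the first window after stopping, a patient who discontinued is absent from the numerator, the denominator and the missing count of the mUFC ≤ ULN proportion. The Month 12–36 figures are therefore conditional on staying on treatment and having a value. The SAP gives no sensitivity analysis for this binary endpoint, although the protocol provides for sensitivity analyses of the efficacy endpoints.

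Neither direction nor size can be fixed from the documents. From a 20% start, the assumed scenarios give 11% to 37%, against 8% to 14% of enrolled patients on drug and controlled. These rest on fixed control status, complete measurement among those still treated, and assumed stopping rates. The phase III rates used as a guide apply to responders who had not up-titrated, a different definition. The illustration shows what the rule can do; it does not forecast the result.

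This should be corrected, but it concerns a descriptive secondary endpoint and leaves the primary safety analysis untouched.

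**What to change.** In SAP 8.2.1.1:

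1. Keep the existing proportion and label it 'among patients still on pasireotide with a value'.
2. For each window, overall and by cohort, add a supplementary proportion labelled 'on pasireotide and controlled'. Its denominator is all FAS patients enrolled long enough before the cut-off to have reached the window.
3. In that proportion, count permanent discontinuation before the window as not meeting the endpoint, and show these stops by recorded reason (unsatisfactory effect, adverse event, other).
4. Show patients on treatment without a value as a separate count.

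The cost is SAP wording and one extra row block per window, from data already collected. The added figure will be lower, and must be read as a composite of staying on drug and being controlled, not as a rate of biochemical control alone.
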